2.3.2. Oral RPV and RPV LA (GSK1265744/GSK1265744 LA)

ORAL RPV

For safety and risk mitigation for oral RPV refer to the RPV local prescribing information [Current Edurant Prescribing Information]

RPV LA

Information about the clinical experience to date and possible risks associated with treatment using RPV LA can be found in the Summary of Data and Guidance for the Investigator section of the IB. Systemic reactions following RPV LA injections have been observed in clinical trials. These occur infrequently (in less than 0.5% of participants) and typically begin to resolve within minutes of the injection, some participants have required supportive care. Where timely PK data has been available, high RPV PK plasma concentrations have been observed which may have resulted from an accidental partial IV injection of RPV. Refer to study protocols for instructions on injection administration. The following risks are considered to be of specific clinical relevance in the context of IM use.

Potential Risk of Clinical Significance	Summary of Data/Rationale for Risk	Mitigation Strategy
Injection Site Reactions	Clinical, experience to date has demonstrated ISRs occur in the majority of exposed participants treated with RPV LA but are generally mild (Grade 1) or moderate (Grade 2) and include events of pain, tenderness, erythema, or nodule formation of several days duration (median duration for individual events <1 week). ISRs may occur more than once in an individual participant receiving multiple injections. Although some Grade 3 ISRs were reported, overall ISRs have been well tolerated and have not to date been associated with an excess of participants' withdrawal due to ISRs. None of the ISRs was serious and no clinical significant complications were reported	Administration advice to minimize risk of poor administration technique giving rise to injection site reactions. Advice on care, monitoring, natural course, and treatment of ISRs given in study documentation. Advice to participants on care of injection site on day/days immediat post administration, use of analgesia, compresses where appropriate. Participants will be closely monitored for ISRs particularly for signs of pain, tenderness, infections, erythema, swelling, induration, or nodules (granulomas or cysts) throughout the study.
		Complications of ISRs such as infections (abscess, cellulitis) and collections of fluid requiring drainage will be monitored Significant ISRs may be photographed and referred to a dermatologist for specialist advice.

Potential Risk of Clinical Significance	Summary of Data/Rationale for Risk	Mitigation Strategy
Rash	Some observations of rash with oral RPV have been reported in clinical studies executed to date (the majority are mild).	 Participants with a Grade 1 or 2 rash will be allowed to continue treatment, depending on the clinical judgment of the investigator. All participants experiencing a Grade 3 or 4 rash should discontinue their antiretroviral (ARV) medication (study medication and background regimen) and be withdrawn from the study. All rash events should be assessed with special attention to systemic symptoms, laboratory abnormalities, or mucosal involvement. Close clinical follow-up, including follow-up of laboratory abnormalities, and appropriate medical intervention, including referral to dermatologist as appropriate, should be instituted for these events; daily follow-up is recommended for 5 days from the onset of the event to monitor for progression of the
		event. See Section 10.6.5.10 for additional guidance on management of rash.
Development of Resistance	Residual concentrations of RPV LA can remain in the systemic circulation of participants who stopped treatment (e.g., for tolerability issues or treatment failure) for prolonged periods (months to more than a year, in some participants) Participants discontinuing a LA regimen may be at risk for developing resistance to RPV many weeks after discontinuing injectable therapy.	After participants stop RPV LA, Oral HAART regimens will be prescribed within one month (- 7 days) after the last dose if interruption is prior to Dose 2 and within 2 months (± 7 days) after the last injection if interruption is following Dose 2, and following consultation with the medical monitor. This would be anticipated to result in continued suppression or rapid re-suppression of HIV-1 RNA thus minimizing the risk of emergent resistance.
		The Sponsor will continue to monitor participants in this study who discontinue the LA regimen prior to local availability of CAB LA+ RPV LA for a minimum of 52 weeks from the time of the last LA administration. Post- commercial local availability, the Sponsor will continue to monitor participants in this study who prematurely discontinue a LA regimen for safety reasons for a minimum of 52 weeks from the time of the last LA administration.

RPV LA should not be co-administered with the following medicinal products, as significant decreases in RPV plasma concentrations may occur (due to CYP3A enzyme induction), which may result in loss of therapeutic effect of RPV LA. consent. - the anticonvulsants carbamazepine, oxcarbazepine, phenobarbital, phenytoin - - the antimycobacterials rifampicin, rifapentine, rifabutin - - the glucocorticoid systemic dexamethasone, except as a single dose treatment - - St John's wort (Hypericum perforatum). Of note, evidence to date indicates that clinically relevant DDIs with RPV LA and other antiretrovirals are unlikely to occur. Oral RPV administration only: Oral RPV administration only:	Potential Risk of	Summary of Data/Rationale for Risk	Mitigation Strategy
(DDIs) medications for RPV and RPV LA, refer to Section 6.6. throughout the study and updates provided as needed via information of the co-administered with the following medicinal products, as significant decreases in RPV plasma concentrations may occur (due to CYP3A enzyme induction), which may result in loss of therapeutic effect of RPV LA. throughout the study and updates provided as needed via information of the anticonvulsants carbamazepine, oxcarbazepine, phenobarbital, phenytoin • the antimycobacterials rifampicin, rifapentine, rifabutin • the glucocorticoid systemic dexamethasone, except as a single dose treatment • St John's wort (Hypericum perforatum). Of note, evidence to date indicates that clinically relevant DDIs with RPV LA and other antiretrovirals are unlikely to occur. Oral RPV administration only:	Clinical Significance		
 -Antacht products containing divarent cations (e.g., aufminum, calcium, and magnesium) must be taken at least 2 hours before or at least 4 hours after RPV. -H2-antagonists must be taken at least 12 hours before or at least 4 hours after taking RPV. -RPV should not be co-administered with proton pump inhibitors, 	Clinical Significance Drug-Drug Interactions	 For a complete listing of permitted and prohibited concurrent medications for RPV and RPV LA, refer to Section 6.6. RPV LA should not be co-administered with the following medicinal products, as significant decreases in RPV plasma concentrations may occur (due to CYP3A enzyme induction), which may result in loss of therapeutic effect of RPV LA. the anticonvulsants carbamazepine, oxcarbazepine, phenobarbital, phenytoin the antimycobacterials rifampicin, rifapentine, rifabutin the glucocorticoid systemic dexamethasone, except as a single dose treatment St John's wort (Hypericum perforatum). Of note, evidence to date indicates that clinically relevant DDIs with RPV LA and other antiretrovirals are unlikely to occur. Oral RPV administration only: -Antacid products containing divalent cations (e.g., aluminum, calcium, and magnesium) must be taken at least 2 hours before or at least 4 hours after RPV. -H2-antagonists must be taken at least 12 hours before or at least 4 hours after taking RPV. 	All participants will be informed of prohibited medications throughout the study and updates provided as needed via informed

Potential Risk of Clinical Significance	Summary of Data/Rationale for Risk	Mitigation Strategy
	Participants discontinuing a LA regimen may be at risk for developing DDIs many weeks after discontinuing injectable therapy.	
Inadvertent Intravenous Injection (Accidental Maladministration)	As with any intramuscular injection, it is possible that RPV LA can be inadvertently administered intravenously instead of intramuscularly possibly resulting in higher than expected concentrations of RPV shortly after injection and lower concentrations thereafter. This could be due to administrator error, improper injection technique and / or improper needle length used based on body type. In addition, HIV-1 viral suppression may not be effective following accidental intravenous maladministration.	 Training will be provided to all sites on proper injection technique. Should IM maladministration be suspected at any time (e.g., suspected under or overdose or inadvertent intravenous [IV] dosing), post dose ECG monitoring and vital signs or any other supportive testing may be obtained at the discretion of the Investigator, and the medical monitor notified. Laboratory samples for safety parameters and HIV-1 RNA will be closely monitored in all participants. Additionally, an unscheduled PK sample may be drawn approximately 2 hours post dosing for future evaluation of RPV concentrations.
Overall Study Related R	isks	
Venipuncture	Participants will be required to have blood samples taken. Risk of bruising, and rarely, infection	Trained personnel will perform venipuncture
Potential Risk of Clinical Significance	Summary of Data/Rationale for Risk	Mitigation Strategy

Potential Risk of Clinical Significance	Summary of Data/Rationale for Risk	Mitigation Strategy
Risk of Treatment Failure	This study employs a novel 2 drug LA ART treatment regimen dosed Q8W for the treatment of HIV-1 infection recently approved EU and under review in other countries. Both IM CAB and RPV have demonstrated antiviral activity in large clinical studies and the two-drug combination dosed Q4W has demonstrated sustained antiviral activity in studies 200056, 201584 and 201585 and in studies (200056 and 207966) when dosed Q8W. Doses of the CAB LA and RPV LA have been selected to achieve exposures that are expected to maintain virologic efficacy on the basis of available data with the oral and LA formulations. Due to administration error, it is possible that a participant could receive an inadequate dose of CAB LA or RPV LA. Sub-therapeutic concentrations of either CAB LA or RPV LA could lead to virologic failure and possibly the development of viral resistance.	Viral loads and CD4+ cell counts will be closely monitored throughout the study (treatment and extension phases), allowing for early detection of failing treatment. Where confirmed virological failure occurs, participants would be discontinued from study drugs and transferred to an oral HAART regimen.

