- At the request of the participant, Investigator, GSK or ViiV Healthcare;
- The participant requires concurrent prohibited medications during the course of the study. The participant may remain in the study if in the opinion of the Investigator and the medical monitor; such medication will not interfere with the conduct or interpretation of the study or compromise the safety of the participant.

Participants must be discontinued from study intervention for any of the following reasons:

- Virologic withdrawal criteria as specified in Section 7.1.6 are met;
- Participant requires substitution of ART;
- Participant requires substitution or dose reduction of CAB LA, RPV LA (oral bridging supply and potential for a second loading dose may be permissible following discussion with the Medical Monitor)
- Liver toxicity where stopping criteria are met and no compelling alternate cause is identified (see Section 10.6.5.1);

- Renal toxicity is met and no compelling alternate cause is identified;
- Corrected QT interval (QTc) >550msec from three or more tracings separated by at least 5 minutes and considered causally related to IP. *Note: ECGs are not routinely conducted in this study.*
- Grade 4 clinical AE considered causally related to study drug;
- Participant has a Grade 3 or higher rash or Grade 2 rash with evidence of systemic involvement and no compelling alternative cause is identified
- Participant withdrew consent

Safety data for all participants who receive any amount of study drug, including participants who withdraw from the study, will be included in evaluations of safety.

If a participant is prematurely or permanently withdrawn from the study, and not continuing into the LTFU, the procedures described in the Schedule of Activities Table for the in-clinic Withdrawal visit are to be performed. Where a participant does not complete a withdrawal visit or enter the LTFU, an in-clinic or remote Safety Follow-Up visit will be conducted 4 weeks after the last dose of study medication when there are ongoing AEs serious adverse events (SAEs) related & not related to study drug and also any laboratory abnormalities that are considered to be AEs or potentially harmful to the participant, at the last on-study visit.

All data from the Withdrawal visit will be recorded, as they comprise an essential evaluation that should be done prior to discharging any participant from the study.

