10.6.4. Grade 4 Toxicity/Adverse Event

- Participants who develop a Grade 4 AE or toxicity must have IP permanently discontinued. However, if the Investigator has compelling evidence that the AE is not causally related to the IP, dosing may continue after discussion with and assent from the Medical Monitor. Participants should be rechecked each week until the AE returns to Grade 2.
- Participants experiencing Grade 4 AEs requiring permanent discontinuation of IP should be followed weekly until resolution of the AE and encouraged to complete the withdrawal and follow-up study evaluations as noted above. Any participant receiving at least one dose of CAB LA and /or RPV LA who discontinue IP / Withdraw will initiate treatment with HAART and enter the Long-Term FollowUp Phase for 52 weeks of follow up.
- Participants with Grade 4 asymptomatic laboratory abnormalities should be investigated for all potential non-drug related causes, and, following discussion with the Medical Monitor, may continue therapy if the Investigator has compelling evidence that the toxicity is not related to IP, with the exception of liver chemistry stopping criteria. An in-clinic follow-up visit will be performed approximately 2-4 weeks after the last dose of study medication if AEs, SAEs, or

laboratory abnormalities considered potentially harmful to the participant are ongoing at the last on-study visit. Isolated Grade 4 lipid abnormalities do not require withdrawal of IP.

Participants should permanently discontinue study drug [and all other concurrent medication(s) suspected in the Investigators causality assessment] for an isolated Grade 3 or 4 rash, except where the etiology of the rash has been definitively diagnosed as NOT attributable to study drug (see below), and the participant should be withdrawn from the study. Participants should be treated as clinically appropriate and followed until resolution of the AE. Every effort should be made to collect as much information as possible about the evolution of the event and any relationship with potentially related medical events (e.g., viral infection) or start of concomitant medication.

The rash and any associated symptoms should be reported as adverse events and appropriate toxicity ratings should be used to grade the events (based on DAIDS toxicity gradings – see Section 10.2).

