However, if the etiology of the rash has been definitively diagnosed as being unrelated to study drug and due to a specific medical event or a concomitant infection or a concomitant non-study medication, routine management should be performed and documentation of the diagnosis provided. In this situation, the study drug should be continued.

Participants in the Follow-Up Phase who are receiving ABC as part of their regimen should be evaluated for the possibility of a clinically suspected ABC HSR and managed appropriately as outlined in the local prescribing information for ABC.

Any participant receiving at least one dose of CAB LA and /or RPV LA who discontinue IP / Withdraw will initiate treatment with HAART and enter the LTFU phase for 52 weeks of follow-up.

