Participants may continue study drug for an isolated Grade 2 rash. However, study drug (and all other concurrent medication(s) suspected in the Investigators causality assessment) should be permanently discontinued for any Grade ≥ 2 rash that is associated with an increase in ALT. The participant should be advised to contact the physician immediately if rash fails to resolve (after more than 2 weeks), if there is any worsening of the rash, if any systemic signs or allergic symptoms develop, or if mucosal involvement develops.

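### For a Grade 3 or 4 rash definitively diagnosed as unrelated to study drug, Protocol Section 2.3.2 says stop and withdraw while Section 10.6.4 says continue; Section 7 uses a third standard

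*Protocol*

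**What the plan says.** Four places in the protocol govern what happens to a participant with rash.

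- **Section 2.3.2**, RPV LA risk table, mitigation strategy. Grade 1 or 2 rash may continue on the investigator's judgment. For higher grades: "All participants experiencing a Grade 3 or 4 rash should discontinue their antiretroviral (ARV) medication". The same sentence extends the stop to any background regimen and requires withdrawal. The entry ends: "See Section 10.6.5.10 for additional guidance on management of rash".
- **Section 7**, list of reasons for which participants must be discontinued from study intervention: "Participant has a Grade 3 or higher rash or Grade 2 rash with evidence of systemic involvement and no compelling alternative cause is identified".
- **Section 10.6.4**, rash text. The default for an isolated Grade 3 or 4 rash is permanent discontinuation and withdrawal, "except where the etiology of the rash has been definitively diagnosed as NOT attributable to study drug (see below"). The text below that sentence says that "if the etiology of the rash has been definitively diagnosed as being unrelated to study drug" and due to a specific medical event, an infection or a non-study medication, the rash is managed routinely and the diagnosis documented. It then says: "In this situation, the study drug should be continued".
- **Section 10.6.5.10**, rash without hypersensitivity symptoms. An isolated Grade 1 or Grade 2 rash may continue. Study drug "should be permanently discontinued for any Grade" 2 or higher rash that comes with a rise in ALT. The section has no attribution exception for Grade 3 or 4 rash.

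**The concern.** These are directive rules for site staff, and for one kind of participant they cannot all be followed. Both possible errors have consequences that the protocol itself describes. Section 2.3.1 notes that long exposure after a CAB injection may complicate the management of a hypersensitivity reaction, and Section 2.3.2 says residual RPV can persist for months to more than a year. In the other direction, under Section 10.6.4 a participant who stops after at least one LA dose starts HAART and enters 52 weeks of follow-up, and under Section 4.3.3 a withdrawn participant may not be re-screened.

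The outcome also reaches the tables. The proportion discontinuing treatment because of adverse events is a secondary endpoint (Protocol Section 3). In the SAP's Snapshot algorithm (Appendix 8), a participant who discontinues for an adverse event without an on-treatment viral load in the Month 12 window is counted as having no virologic data. If sites read different pages, the same event is counted differently.

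**Working it through.** No calculation decides this point. The check is to run the same participant through each section.

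The qualifier in Section 7 can be read in two ways. On **reading (a)** it covers both Grade 3 or higher rash and Grade 2 rash with systemic involvement. On **reading (b)** it covers only the latter. All three cases below are an isolated Grade 3 or 4 rash.

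| Case | Section 2.3.2 | Section 7 (a) | Section 7 (b) | Section 10.6.4 |
|---|---|---|---|---|
| 1. Definitively diagnosed as unrelated, e.g. due to an infection | Stop, withdraw | Mandatory stop not triggered | Mandatory stop | Continue |
| 2. Compelling but not definitive alternative cause | Stop, withdraw | Mandatory stop not triggered | Mandatory stop | Stop permanently, withdraw |
| 3. Alternative cause merely suspected | Stop, withdraw | Mandatory stop | Mandatory stop | Stop permanently, withdraw |

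1. **Case 1 is a direct contradiction.** Sections 2.3.2 and 10.6.4 give opposite instructions whichever way Section 7 is read. On reading (b), Section 7 joins Section 2.3.2 and also contradicts Section 10.6.4.
2. **Case 2 shows different standards.** Section 7 asks for a compelling alternative cause, Section 10.6.4 for a definitive diagnosis. On reading (a) the event falls outside the list of mandatory stops but is still stopped under Sections 2.3.2 and 10.6.4.
3. **Case 3 shows no conflict.** All sections stop the drug.
4. **The cross-reference does not help.** Section 2.3.2 points to Section 10.6.5.10. The exception sits in Section 10.6.4, to which it does not point.
5. **The general toxicity rules differ again.** Sections 10.6.3 (Grade 3) and 10.6.4 (Grade 4) allow dosing to continue on compelling evidence that the event was not caused by study drug, after discussion with the Medical Monitor. The rash exception in Section 10.6.4 sets a higher evidential bar and does not mention the Medical Monitor.
6. **Grade 2.** Section 2.3.2 names neither the stop for systemic involvement (Section 7) nor the stop for an ALT rise (Section 10.6.5.10).

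**Frequency.** Section 10.6.5.10 gives 0.1% for treatment-related Grade 3 rash with RPV. For about 450 patients that is 0.001 × 450 = 0.45 expected events. This only indicates that severe rash is uncommon. The rashes on which the rules diverge are those established as unrelated to drug, and the documents give no rate for them.

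**The case against.** The strongest reply is that Section 2.3.2 is benefit-risk background, Section 7 is a minimum list of mandatory stops, and Section 10.6.4 is the operative guidance with the same default as Section 2.3.2. Part of this stands. Falling outside the Section 7 list is not an instruction to keep dosing, and Section 7 separately lets participants be discontinued for an adverse event. But the Section 2.3.2 text is a mitigation strategy addressed to all participants, nothing ranks it below Section 10.6.4, and its cross-reference leads elsewhere. Setting it aside would still leave Sections 7 and 10.6.4 with different attribution standards.

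Some stronger inferences are tempting, and the documents do not support them:

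- *Every Grade 3 or 4 rash with another suspected cause meets opposite instructions.* A suspicion is neither compelling nor definitive, so every section stops the drug (case 3).
- *Section 10.6.4 is a permissive rule.* Its default is to stop and withdraw; the exception is narrow.
- *The Grade 2 texts contradict one another.* They read mostly as a general rule with narrower exceptions. Section 2.3.2 asks for special attention to systemic symptoms and laboratory abnormalities, Section 10.6.5.10 limits continuation to isolated rash, and Section 10.6.2 warns that the specific toxicities carry exceptions. What remains is that Section 2.3.2 does not state the two stops.
- *The conflict drives the discontinuation endpoint.* That endpoint is secondary and only summarised (Section 9.4.2), and no figure in the documents supports a material effect.

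**Conclusion.** The inconsistency is real but narrow. For a Grade 3 or 4 rash definitively diagnosed as not attributable to study drug, Section 2.3.2 requires stopping and withdrawal while Section 10.6.4 says to continue, and this holds on either reading of Section 7. Section 7 adds a different standard of unclear scope, and Section 2.3.2 is silent on two Grade 2 stops. The conclusion rests on the wording alone and on treating Section 2.3.2 as binding on sites, as its directive language suggests.

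The number of affected participants is likely to be small. Its effect on the count of discontinuations due to adverse events cannot be estimated from the documents. The primary analysis of staff scores is not touched. It merits correction because it is a safety rule that a site cannot follow consistently and the repair is cheap.

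**What to change.** Reconcile Sections 2.3.2, 7, 10.6.4 and 10.6.5.10 into one rash rule, set out by grade and with a single attribution standard. State explicitly whether that standard applies to Grade 3 or higher rash, to Grade 2 rash with systemic involvement, and to rash with an ALT rise, and whether Medical Monitor involvement is needed. Keep the rule in one section and have the others refer to it, correcting the cross-reference in Section 2.3.2. Which rule is right is a clinical decision for the sponsor.

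The cost is protocol wording, carried in an amendment and communicated to sites. No assessment, data collection or planned analysis needs to change.
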